#### 7.1.7 Deaths

All deaths and all AEs resulting in death during the study treatment period or 90 days follow-up period must be reported as SAE.

The convention for recording death is as follows:

- S/AE term: the disease or condition directly leading to death including the most precise cause of death such as hepatic failure or any other cause of death (World Health Organization Medical Certification of Cause of Death, 1979)
- Outcome: fatal
- CTCAE v5 Grade 5
- All relevant clinical and safety information related to death including its time

The only exception is if the cause of death is unknown (ie, sudden or unexplained death), in which case the AE term may be "death" or "sudden death" until the cause of death is determined or if the cause of death will not be possible to be determined. In all these cases, every effort must be made to provide appropriate medical history around the event and pertinent records relating to the fatal outcome.

### 7.1.8 Reporting to Competent Authorities, IECs/IRBs and Other Investigators

The Sponsor will ensure that processes are in place for submission of reports of Suspected Unexpected Serious Adverse Reactions (SUSARs) occurring during the study to the Competent Authorities (CAs), IECs and other Investigators concerned by the IMP.

Suspected AEs are any AEs for which there is a reasonable possibility that the IMPs caused the AE.

As there is no clinical experience yet with KY1044, all SAEs will be reported as unexpected.

Reporting will be done in accordance with the applicable regulatory requirements.

Details of procedures and responsibilities will be documented in the SAE management plan for the study.

### 7.2 Important Medical Procedures to be Followed

#### 7.2.1 Medical Emergencies and Sponsor Contacts

Each patient will be given a card at the enrolment visit and asked to carry it with them at all times in case of an emergency. The card will include the following study information as a minimum: a patient identifier, IMP name and name and 24-hour telephone number of the Investigator (or medically qualified designee).

If the Investigator needs urgent advice a 24/7 telephone line will be available to contact the Medical Monitor. The phone number will be provided in a separate manual.

#### 7.2.2 Guidance for Overdose

Symptomatic overdose (serious or nonserious) with Investigational Medicinal Products (IMPs)

- An overdose of IMP (KY1044) is defined as: increase of at least 30% of the dose to be administered in the specified duration or if the dose is administered in less than half the recommended duration of administration.
- An overdose (accidental or intentional) with the IMP (atezolizumab) is an event suspected by the Investigator or spontaneously notified by the participant and defined as at least twice the intended dose within the intended therapeutic interval, adjusted according to the tested drug.

In the unlikely event that an overdose of KY1044 is administered, the patient will be observed and treated symptomatically.

KY1044 is expected to have a very slow clearance leading to a half-life  $(t_{2})$  of approximately 3 weeks. If severe adverse reactions occur after an overdose of KY1044, then plasmapheresis to reduce the drug exposure may be considered.

There is no information on atezolizumab overdose. Treat as clinically indicated.

Cases of overdose should be documented as protocol deviations in the protocol deviation log.

#### 7.2.3 Protocol Deviations

Any inadvertent protocol deviations that occur during the conduct of the study must be fully documented by the Investigator and the Sponsor notified.

### 7.2.4 Pregnancy

All pregnancies and their subsequent outcome (spontaneous miscarriage, elective termination, ectopic pregnancy, normal birth or congenital abnormality) should be reported to PRA Drug Safety.

### 7.2.4.1 Maternal Exposure

If a patient becomes pregnant during the course of the study IMP should be discontinued immediately.

Pregnancy itself is not regarded as an adverse event unless there is a suspicion that the study treatment under investigation (IMP), may have interfered with the effectiveness of a contraceptive medication. Congenital abnormalities/birth defects and spontaneous miscarriages will be reported and handled as SAEs. Elective abortions without complications should not be handled as AEs. The outcome of a pregnancy should be followed up and documented even if the patient is withdrawn from the study.

If a pregnancy occurs during exposure to study treatment or in the 90 days after discontinuing study treatment, then Investigators or other site personnel inform PRA Drug Safety within one day ie, immediately but no later than the end of the next business day of when he or she becomes aware of it.

PRA Drug Safety works with the Investigator to ensure that all relevant information is provided to PRA Drug Safety as soon as it is available for SAEs (see Safety Management Plan) and within 30 days for all other pregnancies not considered to be SAEs.

The same timelines apply when outcome information is available.

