## c. Phase 2 KY1044 in combination with atezolizumab:

Patients with advanced/metastatic malignancies in the selected indications below, and/or indications which have shown promising activity in Phase 1:

- NSCLC (anti-PD-(L)1 therapy naïve and pre-treated between 1 and 2 prior lines of systemic therapy for advanced disease)
- Gastric/Esophageal (anti-PD-(L)1 therapy naïve and pre-treated)
- Recurrent and/or metastatic HNSCC (anti PD (L)1 therapy naïve and pre treated between 1 and 2 prior lines of systemic therapy for advanced disease)
- Cervical (anti-PD-(L)1 therapy naïve and pre-treated)
- Indications, in which signs of anti-tumor activity has been observed in Phase 1 with KY1044 in combination with atezolizumab
- 5. Prior therapy with anti-PD-(L)1 inhibitors is allowed provided any toxicity attributed to prior anti-PD-(L)1-directed therapy did not lead to discontinuation of therapy
- 6. Eastern Cooperative Oncology Group (ECOG) Performance Status 0-1
- 7. Life expectancy longer than 12 weeks.
- 8. Must have a site of disease amenable to biopsy, and be a candidate for tumor biopsy according to the treating institution's guidelines. Patient must be willing to undergo a new tumor biopsy at screening, and during therapy on the study
- 9. Females of childbearing potential must be using two highly effective contraceptive measures for the duration of study participation and for at least 5 months after discontinuing study treatment, or longer if the half-life of KY1044 is observed to exceed that of

atezolizumab (see Section 5.8). Females must not be breast feeding and must have a negative pregnancy test prior to start of dosing or must have evidence of non-childbearing potential by fulfilling one of the following criteria at screening:

- Post-menopausal defined as aged ≥50 years and amenorrhoeic for at least 12 months following cessation of all exogenous hormonal treatments
- Women less than 50 years old would be considered postmenopausal if they have been amenorrhoeic for at least 12 months following the cessation of exogenous hormonal treatments, and have serum follicle-stimulating hormone and luteinizing hormone levels in the postmenopausal range for the institution
- Documentation of irreversible surgical sterilization by hysterectomy, bilateral oophorectomy or bilateral salpingectomy but not tubal ligation

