- 10. For the duration of study participation and for at least 5 months after discontinuing study treatment, or longer if the half-life of KY1044 is observed to exceed that of atezolizumab, sexually active males must use barrier contraception (ie, condoms). See Section 5.8.

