### 5.8 Lifestyle Restrictions

The following restrictions (according to the CTFG (Clinical Trial Facilitation Group) Recommendations Related to Contraception and Pregnancy Testing in Clinical Trials in Women of Childbearing Potential apply while the patient is receiving study treatment and for the specified times before and after:

1. Females of childbearing potential must use two highly effective methods of contraception from the time of screening until 5 months after discontinuing study treatment, or longer, depending on the PK of KY1044 (contraception must be maintained for at least 5 half-lives).

Acceptable methods of contraception include true sexual abstinence when this is in line with the preferred and usual lifestyle of the patient, tubal ligation, hormonal contraceptives that are not prone to drug-drug interactions (for example Levonorgestrel Intra Uterine System [Mirena], medroxyprogesterone injections [Depo Provera]), copper-banded intra-uterine devices and vasectomized partner. Periodic abstinence (eg, calendar, ovulation, symptothermal, post-ovulation methods), declaration of abstinence for the duration of a trial, and withdrawal are not acceptable methods of contraception. All methods of contraception must be used in combination with the use of a condom by their male sexual partner for intercourse.

2. Male patients must avoid unprotected sex with all sexual partners (by use of condoms) during the study, and for a washout period of at least 5 months after the last dose of IMP, depending on the PK of KY1044. A condom is also required to be used by vasectomized men in order to prevent delivery of the drug via seminal fluid. Where a sexual partner of a male participant is a woman of childbearing potential, patients must avoid procreation for at least 5 months after completion of treatment with IMP. Patients must refrain from donating sperm from the start of dosing until at least 5 months after discontinuing study treatment. If male patients wish to father children during the study period they should be advised to arrange for freezing of sperm samples prior to the start of study treatment.

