#### 7.2.4.2 Paternal Exposure

Pregnancy of a patient's partner is not considered to be an adverse event. However, any conception occurring from the date of dosing until 90 days after dosing will be reported to PRA Drug Safety and followed up for its outcome.

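### The 90-day pregnancy windows in Protocol 7.2.4.1 and 7.2.4.2 are about two months shorter than the contraception period and do not fit the open-ended rule that heads Section 7.2.4.

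*Protocol*

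**What the plan says.** Three reporting provisions sit together in Protocol 7.2.4:

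- **Opening rule (7.2.4).** The duty to notify the safety vendor covers "All pregnancies and their subsequent outcome". No time limit is given.
- **Maternal exposure (7.2.4.1).** Prompt notification, by the close of the next working day at the latest, is tied to one case: "If a pregnancy occurs during exposure to study treatment or in the 90 days after discontinuing study treatment". Outcome follow-up is stated separately, without a window, and applies even after withdrawal from the study.
- **Paternal exposure (7.2.4.2).** Both reporting and outcome follow-up are confined to "any conception occurring from the date of dosing until 90 days after dosing".

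The contraception rules run longer:

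- **Women (4.2, criterion 9).** The requirement is "two highly effective contraceptive measures for the duration of study participation and for at least 5 months after discontinuing study treatment". A condition on the KY1044 half-life can extend it.
- **Men (4.2, criterion 10).** The period reads "For the duration of study participation and for at least 5 months after discontinuing study treatment, or longer", again subject to that half-life condition. Section 5.8 adds a separate rule for men whose partner could become pregnant: "patients must avoid procreation for at least 5 months after completion of treatment with IMP".
- **Basis (5.8, in the rule for women).** "contraception must be maintained for at least 5 half-lives".

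Section 7.2.2 expects a KY1044 half-life of about 3 weeks. Section 7.1.6 makes pregnancy an adverse event of special interest for both products and gives it no time window of its own.

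**The concern.** The protocol asks patients to avoid conception for at least 5 months after treatment, but its two specific reporting rules stop at 90 days. A site applying Section 7.2.4 to a pregnancy in month 4 or 5 finds an opening sentence that says to report it and subsections that no longer mention it.

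Little else in the schedule would bring such a case to light. In Tables 6-1 and 6-2 pregnancy testing ends at the end-of-treatment visit, and the safety follow-up column has none. Adverse event collection ends 90 days after the last dose (7.1). Later contact is for survival status. Patients still having tumor assessments also have relevant adverse event data recorded (8.2.2), but 7.2.4.1 generally does not count a pregnancy as an adverse event and 7.2.4.2 does not count a partner's pregnancy as one.

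At stake is the completeness of a small body of safety information. This is a first-in-human antibody, exposed pregnancies will be few, and each outcome carries weight.

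**Working it through.** The plan gives no figure of its own for the difference, so there is nothing to reproduce first. The check is interval arithmetic.

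**Inputs**
- Reporting windows: 90 days (7.2.4.1 and 7.2.4.2).
- Minimum contraception period: 5 months (4.2 and 5.8).
- Month length: 30.4375 days, the SAP's own conversion (SAP 8.6.3 to 8.6.5).
- Expected KY1044 half-life: 3 weeks = 21 days (7.2.2).
- Pharmacokinetic rule: at least 5 half-lives (5.8).

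**Against the 5-month minimum**
- 5 × 30.4375 = 152.2 days.
- 152.2 − 90 = 62.2 days, and 62.2 / 30.4375 = 2.04 months.
- 62.2 / 152.2 = 41% of the minimum period.
- Depending on the month convention, 5 months is 150 to 153 days, so the difference is 60 to 63 days.

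**Against 5 half-lives**
- 5 × 21 = 105 days, and 105 − 90 = 15 days.
- 90 / 21 = 4.3 half-lives covered.
- 90 / 5 = 18: the windows would reach 5 half-lives only if the half-life were 18 days or less.
- 152.2 / 5 = 30.4: above a half-life of about 30 days, 5 half-lives exceeds 5 months and the difference grows beyond 62 days.

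**What each rule does after day 90**

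| Case | Opening rule, 7.2.4 | Specific rule |
|---|---|---|
| Patient becomes pregnant | Reportable, no deadline | One-day notification in 7.2.4.1 no longer applies; outcome follow-up still does |
| Partner conceives | Reportable if the opening rule is read to cover partners | Outside the conception limit in 7.2.4.2 for both reporting and follow-up |

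The partner case is a conflict between two rules. The maternal case is a missing deadline.

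**The case against.** A reader might infer that pregnancies after day 90 are not reportable and would go unreported or unfollowed. The documents do not support that.

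- The opening sentence of 7.2.4 has no time limit and heads both subsections.
- The 90 days in 7.2.4.1 set only the expedited deadline. They do not exempt later pregnancies, and the outcome rule there has no window.
- Section 7.2.4.1 refers to a Safety Management Plan, which is not among the documents and may say more.
- The contraception period may be precautionary. Section 5.8 does not call it a risk window for reporting, so the 41% measures time outside the explicit windows and is not a share of pregnancies missed.
- The 3-week half-life is an expectation stated in the overdose guidance, and on it the shortfall is only 15 days.
- The inconsistency touches no endpoint, analysis or dose decision, and few cases are expected.

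All of this stands, and it limits the point to one of inconsistent rules. It does not remove it. The partner rule selects by conception date which cases are reported and followed, and a site would naturally take that as the working limit. The late maternal case has no deadline in 7.2.4. One could carry over the 24-hour reporting that 7.1.6 requires for other events of special interest, but its sentence on pregnancy states no clock and does not mention the one-day rule.

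**Conclusion.** The point holds as an inconsistency in safety reporting. Both explicit windows end about 62 days (60 to 63) before the minimum contraception period does, and 15 days before 5 half-lives if the half-life is 21 days as expected. After day 90 a partner conception falls outside the stated rule in 7.2.4.2, contrary to an opening rule without limit, and a maternal pregnancy is reportable without a notification deadline in 7.2.4. With no later pregnancy test and no routine adverse event collection, such cases may be missed or reported late. How often cannot be derived from the documents.

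The 62 days rest only on the stated 5 months and the month convention. The 15 days also rest on the expected half-life. No view is taken on what the contraception period should be.

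**What to change.** Reconcile the opening rule of 7.2.4 with 7.2.4.1 and 7.2.4.2, and all three with 5.8:

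- Define the maternal notification window and the partner reporting and follow-up window by reference to the contraception period in 5.8, so that neither is shorter and both move with it if KY1044 pharmacokinetics lengthen it.
- State whether the opening rule covers partner pregnancies, and what deadline applies to any pregnancy that becomes known after the window closes.
- State how the one-day notification relates to the status of pregnancy as an event of special interest in 7.1.6.
- Carry the same wording into the safety management plan.

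Contraception, dosing and treatment rules are not changed. The cost is protocol and safety-plan wording and very few additional reports.

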#### 7.2.4.2 Paternal Exposure

Pregnancy of a patient's partner is not considered to be an adverse event. However, any conception occurring from the date of dosing until 90 days after dosing will be reported to PRA Drug Safety and followed up for its outcome.

### 8 WITHDRAWAL OF PATIENTS FROM TREATMENT AND/OR THE STUDY

Patients are free to withdraw from participation in the study at any time, without prejudice to their further care. In some circumstances, patients may be discontinued from study treatment but continue certain study assessments, as described in Section 8.1.

The Investigator should discontinue study treatment for a given patient if, on balance, he/she believes that continuation would be detrimental to the patient's well-being.

Study treatment may be discontinued and/or patients may be withdrawn from the study under the following circumstances:

- 1. Withdrawal of consent (see Section 8.1.1)
- 2. Severe non-compliance with the protocol as judged by the Investigator
- 3. Patients incorrectly initiated on study treatment (eg, patient has been determined to have met one or more of the exclusion criteria for study participation at study entry and continuing study treatment might constitute a safety risk).

- 4. AEs that, in the opinion of the Investigator or the Medical Monitor, contraindicate further dosing. (Patients on combination therapy who need to discontinue KY1044 due to AEs, also need to discontinue atezolizumab. In the case that a patient needs to discontinue atezolizumab due to acute infusion reactions or ADAs, KY1044 may be continued after discussion with the Medical Monitor)
- 5. Pregnancy
- 6. Disease progression, (unless, in the opinion of the Investigator, the patient is still receiving clinical benefit, whereby the patient will be treated until the confirmatory progressive disease per iRECIST (Note: patients with rapid tumor progression or with symptomatic progression that requires urgent medical intervention will not be eligible to continue to receive treatment)
- 7. Study terminated by the Sponsor (see Section 3.7)
- 8. 48 months of treatment
- 9. Lost to follow-up

Regardless of the reason for discontinuation, if possible, all patients should undergo End of Treatment procedures and enter the 90 days safety follow-up period. After the safety follow-up period, patients will have their End of Study visit (Section 8.2). All data available for the patient at the time of withdrawal and all reasons for withdrawal, must be recorded in the eCRF.

# 8.1 Follow-up of Patients Off Treatment

If a patient needs to withdraw from study treatment for AEs or other safety reasons (reasons 3 and 4 above), but does not have disease progression, they will continue with tumor progression assessments in accordance with the study schedule until they progress as per iRECIST or until they start another anti-cancer therapy or when the overall end of the study is reached. Patients who withdraw consent to treatment but who accept continued monitoring (see Section 6.2.1) will also continue in the same way. Continuation of patients who stop treatment for reasons of non-compliance should be discussed between the Investigator and the Medical Monitor.

All patients (all reasons 1 to 6 listed above) will be followed up at 3 monthly intervals (telephone followup is acceptable) to obtain survival information after the start of treatment. These data will be recorded in eCRF.

#### 8.1.1 Withdrawal of Informed Consent

A patient who withdraws consent will always be asked about the reason(s) and assessed for the presence of any AEs. If possible, AEs will be followed up as described in Section 7. However, it is at the patient's discretion to withdraw from treatment or from the study without giving any reason.

If consent is withdrawn, the patient will not receive any further study treatment. The patient will be specifically asked if they are withdrawing consent to further participation in the study including any further assessment for disease progression or follow-up of survival information.

Note that the patient may be offered additional tests or tapering of certain treatments (co-medication) if withdrawn for safety.

The Sponsor will continue to retain and use all research results that have already been collected for the study evaluation. All biological samples that have already been collected may be

retained and analyzed at a later date for the fulfilment of the assessments defined in this protocol.

#### 8.1.2 Lost to Follow-up

If a patient fails to return for study assessments for unknown reasons, every effort (eg, telephone calls, e-mail, letter) should be made to contact them. Patients will be considered lost to follow-up only if no contact has been established by the time the study is completed such that there is insufficient information to determine the patient's status at that time.

Note: patients who refuse to continue participation in the study, including phone contact, should be documented as "withdrawal of consent" rather than "lost to follow-up." Investigators should document attempts to re-establish contact with missing patients throughout the study period.

# 8.2 End of Treatment and End of Study Procedures

Patients discontinuing treatment or withdrawing from the study should return for the End of Treatment (EOT) assessments as soon as possible and latest within 21 days of the last dose of study treatment or within 21 days of the decision to discontinue study treatment, and then enter the follow-up period as indicated in (Section 8.2.1).

If the decision to discontinue the patient occurs at a regular scheduled visit, that visit may become the EOT visit rather than having the patient return for an additional visit. The eCRF should be completed, giving the reason for stopping the study treatment.

### 8.2.1 Safety Follow-up Visit

If possible, all patients will return for the safety follow-up visit 90 days after the last dose of study treatment. Assessments will be performed as per schedule of assessments (see Table 6-1 and Table 6-2).

#### 8.2.2 Follow-up Period

All patients must have 90 days safety follow-up evaluations after the last dose of study treatment, including tumor or survival assessments. Evaluations should be performed according to the schedule of assessments, and data collected added to appropriate eCRF pages.

Patients who discontinue study treatment and do not have progressive disease per RECIST 1.1/iRECIST, but continue with study assessments will return for tumor assessments (Section 6.2.1) according to the study schedule. Any relevant adverse event data reported during study visits will be recorded. No other study procedures will be performed. Tumor assessments will stop when disease progression is confirmed (RECIST 1.1), the patient commences further treatment for their malignancy, or when the overall end of the study is reached. The date at which tumor monitoring is discontinued must be recorded. After discontinuation of tumor assessments patients will continue to be followed up for survival status at 3-monthly intervals.

All patients who do not withdraw consent for the study will be followed up for survival unless they are lost to follow-up or the overall end of the study has been declared.

Property of the Sanofi Group - strictly confidential

